# 9.5 Dose, method of administration, dosing regimen, and duration of therapy

## 9.5.1 Use of the investigational product RPH-104

RPH-104 is administered to patients randomized to one of the RPH-104 groups. The dose of RPH-104 for administration to a patient is selected based on information on the patient's therapy group.

To administer RPH-104 4 mg to a patient, 0.1 mL of RPH-104 solution is injected to the patient. To administer RPH-104 20 mg to a patient, 0.5 mL of RPH-104 solution is injected to the patient. To administer RPH-104 40 mg, 1 mL of RPH-104 solution is injected to the patient. To administer RPH-104 80 mg, 2 mL of RPH-104 solution is injected to the patient. To administer RPH-104 160 mg, the patient received two injections of 2 mL RPH-104 solution at different injection sites (Table 9.1).

RPH-104 is injected subcutaneously into the anterior abdominal region in one of the areas indicated in Figure 9.1.

CONFIDENTIAL P. 44 of 84

	U
Treatment group	Volume of RPH-104 solution for administration to the patient
RPH-104 4 mg	0.1 mL
RPH-104 20mg	0.5 mL
RPH-104 40 mg	1 mL
RPH-104 80mg	2 mL
RPH-104 160 mg	Two 2 mL injections at different injection sites

Table 9.1 Injected volume of RPH-104 to patients

[figure not shown]

Figure 9.1 Areas of the anterior abdominal wall where RPH-104 should be administered.

## 9.5.2 Voltaren® (diclofenac) intake

Voltaren® (diclofenac) is given to patients randomized to the Voltaren® (diclofenac) group.

On the first day of therapy, Voltaren® (diclofenac) is dispensed in an amount sufficient to take the drug until the end of the therapy period. The patient takes the first dose of the drug at the study site. Patients who, by the decision of the Investigator, continue to participate on an outpatient basis subsequently take the drug at home on their own in accordance with the study protocol. Hospitalized patients continue to take the drug in a hospital setting until discharge.

Patients take Voltaren® (diclofenac) orally, at a dose of 50 mg 3 times a day for 3 days, then 25 mg 3 times a day for 9 days (12 days in total).

Voltaren® (diclofenac) will be used with Ortanol® (omeprazole), see Section 9.8.1.

#### 9.5.3 Duration of treatment

In all cases, RPH-104 is administered as a single injection; in the case of a 160-mg dose, the drug is administered as two consecutive 80 mg injections at different injection sites.

The duration of therapy with Voltaren® (diclofenac) is 12 days.

The duration of use of Voltaren® (diclofenac) was selected based on the ACR guidelines for the management of acute gout attacks, according to which the use of NSAIDs at a full dose (if necessary) is indicated until the gout attack completely resolves [17]. According to the classification criteria for gout, a gout attack can last for up to 14 days, consequently, drugs that

CONFIDENTIAL P. 45 of 84

relieve a gout attack are indicated during this time [18]. A stepwise approach to relieve a gout attack is used with NSAIDs. In this case, NSAIDs are used at a full dose during the first 3 days, then at a lower dose in the next 7 days [19]. According to an article on a phase III study of rilonacept, for the relief of an acute gout attack, the reference product from NSAIDs was used at the full dose for 3 days (150 mg per day), then at a lower dose (75 mg per day) for 9 days [20]. In accordance with the Voltaren® (diclofenac) labeling, the recommended initial dose of the drug is 150 mg per day and 75-100 mg per day for long-term therapy. In this study, Voltaren® (diclofenac) will be used as a reference product in the first 3 days at the full dose of 150 mg per day, then at a lower dose of 75 mg per day for the next 9 days.

By the decision of the investigator, patients can be hospitalized after the use of the investigational products. Patients who, in the investigator's opinion, are not eligible for hospitalization, are followed up for at least 3 hours after the investigational product administration, after which they can leave the study site and continue to participate in the study with all assessments performed on an outpatient basis.

## 9.6 Overdose with the sponsor's investigational product

Cases of RPH-104 overdose are not known. Symptomatic treatment should be used in the event of an overdose.

# 9.7 Compliance assessment

Patients treated with Voltaren® (diclofenac) are given diaries to record the date, time and dose of Voltaren® (diclofenac) taken. All missed doses should be recorded in the Patient's Diary.

The information on the number of Voltaren® (diclofenac) tablets dispensed to and received from the patient, as well as information from the patient's diary is recorded. It is automatically calculated using the formula: the number of tablets taken by the patient/the number of tablets that the patient had to take \* 100%.

If, based on the results of compliance assessment, the patient took less than 80% of the prescribed dose of Voltaren® (diclofenac), the investigator must discuss with the sponsor the appropriateness of the patient's further participation in the study and the possible premature discontinuation of the patient from the study.

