- 1. At pre-screening, the patient is informed about the study procedures, signs the informed consent to participate in the pre-screening, and is given the patient information sheet with informed consent form describing the main study for familiarization.
- 2. Screening procedures must be performed within 24 hours and the patient is randomized during this time. If necessary (in exceptional cases), the screening period can be extended, while randomization had to be carried out no later than 120 hours (5 days) after the onset of an attack.

CONFIDENTIAL P. 20 of 84

- 3. Visits to the study site on Study Days 10, 18 and 22 are required for patients receiving RPH-104; Patients receiving Voltaren® (diclofenac) do not have to come to the study site, but they must fill out the patient diary and patient questionnaires on these days (pain in the assessed joint, patient global assessment of efficacy).
- 4. Informed consent to participate in the study must be obtained and the informed consent form for participation in the study be signed prior to starting any study procedure.
- 5. This includes date of birth, sex, race, weight, height, body mass index, and information on alcohol consumption.
- 6. The patient is given questionnaires at the visits to record pain intensity in the assessed joint on the visual analogue scale (VAS), patient global assessment of efficacy, and scores of the health assessment questionnaire.
- 7. The VAS must be completed twice: the first time at the screening to assess the patient's eligibility and the second time before randomization to obtain a baseline value. Re-assessment of pain intensity in the assessed joint must be performed immediately (within 1 hour) before randomization.
- 8. Assessment of pain intensity and global efficacy assessment must be performed prior to taking blood samples. It is necessary to hand over a questionnaire to the patient for assessment of pain intensity and global efficacy assessment after 15, 30, 45 minutes, (interval  $\pm$  5 min) 1 and 1.5 hours (interval  $\pm$  10 min) after the use of the investigational products.
- 9. The physician assesses the degree of swelling, tenderness, erythema and movement restriction in the assessed joint using the categorical scales specified in this protocol.
- 10. hs-CRP, serum amyloid protein A, cytokines, HIV, HBsAg, HCV Ab, T-SPOT.TB tests, pharmacokinetics and anti-drug antibodies (including the test for neutralizing antibodies) are performed in central laboratories.

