- 17. Chest X-ray in 2 views is performed at screening if the patient does not have results of chest X-ray in 2 views or fluorography of the chest in 2 views or chest CT performed within 3 months before the expected date of the first injection of the investigational product;
- 18. Serious adverse events are recorded from the time of signing the informed consent to participate in the study. Other adverse events are recorded from the time of administration to the patient (the first intake by the patient) of the investigational product.
- 19. In patients receiving RPH-104, the assessment of injection site reactions is carried out 15, 30, 45 minutes (interval ± 5 min) after administration and then in accordance with the table of study procedures. The physician assesses the presence of tenderness, redness, swelling, induration, hemorrhage and itching at the RPH-104 injection site. The patient is assessed for these reactions at each visit. They are recorded as adverse events.
- 20. Voltaren® (diclofenac) and Ortanol® (omeprazole) are dispensed only for patients receiving Voltaren® (diclofenac).
- 21. In the diaries, patients record information about the development of adverse events and changes in concomitant therapy (discontinuation or dose change) or use of new concomitant therapy. Patients receiving Voltaren® (diclofenac) are also given additional diaries to record information about the use of Voltaren® (diclofenac). The diaries are filled in by patients when they are outside the study site.
- 22. Blood sampling for T-SPOT.TB test should be carried out either at screening, or during the time the patient is in the hospital.
- 23. Urine analysis includes: color, transparency, specific gravity, pH level, glucose, protein, ketone bodies, bilirubin, urobilinogen, nitrites. Analysis of urine sediment includes: leukocyte count, erythrocyte count, epithelial cell count with cell type, and bacterial count.
- 24. Information is collected about all previous therapy for the primary disease—gout, information about other prior therapy is collected for a period of 30 days before the start of screening.

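### Low diclofenac compliance can lead to study discontinuation in the comparator arm only, and Section 9.7 computes compliance as a tablet count while stating its 80% limit as a share of dose

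*Combined protocol and SAP*

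**What the plan says.** Section 9.5.2 gives the diclofenac course as "50 mg 3 times a day for 3 days, then 25 mg 3 times a day for 9 days". The whole supply "is dispensed in an amount sufficient to take the drug until the end of the therapy period" on the first day.

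Section 9.7 defines compliance, as a percentage, by "the number of tablets taken by the patient/the number of tablets that the patient had to take". The limit that follows is expressed differently: "If, based on the results of compliance assessment, the patient took less than 80% of the prescribed dose of Voltaren® (diclofenac"). Below it, the investigator has to discuss with the sponsor whether the patient should go on, including "the possible premature discontinuation of the patient from the study". No calculation window is given.

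Section 8.1 lists no compliance criterion for withdrawal. Its nearest item is a significant protocol deviation agreed with the sponsor, which applies to every arm. The same section says that rescue medication, prohibited drugs and missed visits are generally not grounds for discontinuation. Section 10.3 sets a minimum list for the early-withdrawal visit, and pain VAS is not on it. Section 13.1.6 replaces missing efficacy values with baseline from the time of withdrawal. RPH-104 is given once, as a single injection or two consecutive ones (9.5.3), so no compliance percentage applies to it.

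**The concern.** Two things do not fit together.

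First, the percentage is a count and the limit is a dose. The course uses two strengths, so the two measures need not agree on who is below 80%.

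Second, the consequence is discontinuation from the study, not merely from the drug, and it can reach only comparator patients. A patient who takes rescue triamcinolone or a prohibited analgesic is normally kept under observation. A patient who misses diclofenac tablets may not be. Once such a patient leaves, pain is no longer measured and the missing-data rule can insert baseline, that is, no improvement. Where the patient had in fact improved, this lowers the apparent diclofenac response and favours RPH-104 in the pairwise differences planned in 13.5.2 and 13.5.3. The loss is avoidable and one-sided.

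**Working it through.** **Inputs.** Regimen: 9.5.2. Strengths of 25 and 50 mg: 9.1. Formula and limit: 9.7. VAS times: 6.1.2. Withdrawal visit: 10.3. Imputation: 13.1.6. Enrolment: 6.2, 6.3.1 and 13.7. Assumption: one tablet per dose.

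**1. The course.** 3 × 3 = 9 tablets of 50 mg = 450 mg; 3 × 9 = 27 tablets of 25 mg = 675 mg. Total: 36 tablets, 1125 mg. This reproduces the plan's 150 mg/day (3 × 50) and 75 mg/day (3 × 25) over 3 + 9 = 12 days. The first three days carry 9/36 = 25% of the tablets but 450/1125 = 40% of the dose.

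**2. Count against dose, over the whole course.** Let a be the 50 mg tablets missed and b the 25 mg tablets missed.

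- By count: (36 − a − b)/36, below 80% when a + b ≥ 8.
- By mg: (1125 − 50a − 25b)/1125, below 80% when 50a + 25b > 225.

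| Missed | By count | By mg |
|---|---|---|
| a = 5, b = 0 | 31/36 = 86.1% | 875/1125 = 77.8% |
| a = 7, b = 0 | 29/36 = 80.6% | 775/1125 = 68.9% |
| a = 0, b = 9 | 27/36 = 75.0% | 900/1125 = 80.0% |

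Of 10 × 28 = 280 combinations, 12 fall on opposite sides of 80%: 9 pass by count and fail by mg, and 3 do the reverse. The first dose is taken at the site, so a = 9 cannot occur in a treated patient. That leaves 9 × 28 = 252 combinations, with the same 12 disagreements. These are counts of possibilities, not probabilities.

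**3. What a discontinuation would remove.** Section 6.1.2 lists 11 post-baseline VAS points up to 72 hours and 8 later, 19 in all.

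- *Whole-course reading.* The course ends on Day 12. On Days 10, 18 and 22, "Patients receiving Voltaren® (diclofenac) do not have to come to the study site", so the first required visit after the course is Day 15. The points then at risk are Days 18, 22, 29 and 45, or 4 of 19. The 72-hour value is already recorded.
- *To-date reading.* Diaries are collected at the Day 2, 3, 4, 5 and 6 visits (10.2). If three tablets are due by 24 hours, one missed gives 2/3 = 66.7%. If six are due by 48 hours, two missed give 4/6 = 66.7%. A discontinuation then would precede the 72-hour VAS, and carrying baseline forward makes that patient's primary change 0. If the change would otherwise have been D mm, the mean of a 14-patient arm moves by D/14. For assumed D of 20, 40 and 60 mm, the shift is 1.4, 2.9 and 4.3 mm per such patient.

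**4. How many patients.** The 47 interim patients have completed participation, so a change to the discontinuation rule affects only later enrolment: 85 − 47 = 38 patients. At 2:2:2:2:1 the expected number on diclofenac is 38/9 = 4.2. The possible range is 0 to 7, since Period 2 has seven diclofenac places. If the interim report becomes final (Section 4 allows this), the number is 0.

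**The case against.** The strongest reply is that the asymmetry comes from the treatments: a 12-day oral course can be under-taken and an injection at the site cannot. Section 9.7 requires only a discussion, 8.1 adds no compliance criterion, and the efficacy population in 13.1.1 has no compliance condition. The trial is open-label and exploratory, and 13.7 plans no formal testing. All of this stands and keeps the point small. It does not explain why missed tablets should put follow-up in question when rescue and prohibited drugs generally do not.

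It can also be said that on a to-date count up to 72 hours all nine tablets due are 50 mg, so count and mg agree. That is correct, and they would also agree if the early doses were given as two 25 mg tablets. Neither point touches the discontinuation clause, and the to-date reading moves a possible discontinuation ahead of the primary measurement.

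A reader might go further and infer that the compliance figure conceals poor early intake, so that the 72-hour comparison cannot be interpreted. On a whole-course count, missing three of the first nine tablets still scores 33/36 = 91.7%. The documents do not support calling this an error. Section 9.7 fixes no window. The diary records date, time and dose and is collected on Day 4. Inpatient doses fall outside it ("The diaries are filled in by patients when they are outside the study site", whereas "Hospitalized patients continue to take the drug in a hospital setting until discharge"), but in-patient records are source documents under 14.1. Individual values are to be listed (13.1), and further analysis detail is deferred to a separate statistical analysis plan that was not available here. A 0 to 72 hour summary is optional.

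**Conclusion.** The point holds as a minor, cheaply corrected weakness. Section 9.7 applies a tablet ratio as if it were a share of dose, and it opens a discretionary discontinuation that can reach only the comparator arm, against the retention approach of 8.1.

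The tablet and mg measures rarely disagree (12 of 280 combinations), and the disagreement depends on one tablet per dose. The discontinuation clause could cost up to 4 of 19 VAS points per affected patient on the whole-course reading, or the 72-hour value on a to-date reading. About 4 future diclofenac patients are exposed to it (range 0 to 7). Scoring the later points as unimproved further assumes that 13.1.6, written for the main efficacy analysis, also covers those time points; otherwise they are simply missing.

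It would be tempting to read this as a threat to the primary result. The documents do not support that. Discontinuation is not automatic, no frequency of under-compliance is given, and on the whole-course reading, which is the more natural one, the 72-hour value is already in hand.

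**What to change.** 1. In 9.7, delete study discontinuation as a consequence of under-compliance, and state that these patients complete all scheduled assessments.
2. In 8.1, state that under-dosing with diclofenac alone is not a reason for withdrawal.
3. In 9.7, calculate the 80% figure as mg taken divided by mg prescribed, and state the window it covers. Use the diary for outpatient doses and site or hospital records for the rest.

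The cost is a few sentences and one derived variable from records already kept. The downside is that some poorly compliant comparator patients stay in follow-up, but the efficacy population already includes them. Items 1 and 2 matter only if enrolment continues. A descriptive 0 to 72 hour compliance figure could be added from the same records if wanted.

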## 9.8 Previous and concomitant therapies

## 9.8.1 Orthanol® (omeprazole)

In order to prevent damage to the gastric and duodenal mucosa caused by Voltaren® (diclofenac), all patients receiving Voltaren® (diclofenac) will simultaneously take Ortanol® (omeprazole) as follows: 20 mg, orally daily before breakfast throughout the course of Voltaren® (diclofenac) treatment.

Method of administration of Ortanol® (omeprazole): orally, with a sufficient amount of liquid. The capsule must be swallowed whole. If the patient cannot swallow the capsule whole, it is possible to dissolve its contents in a small amount of water or fruit juice (for example, apple or orange). The capsule may not be dissolved in carbonated drinks or used with milk. The resulting solution of the drug should be drunk immediately after preparation, washed down with an additional ½ glass of water.

On the first day of therapy in the study, it is possible to take it regardless of meals and at a later time.

#### 9.8.2 Rescue therapy for a gout attack

Patients who do not tolerate pain will receive the rescue medication 2 hours after the first use of the investigational product to intensify therapy. The rescue medication is triamcinolone 40 mg

CONFIDENTIAL P. 46 of 84

intramuscularly. Before administration of the rescue medication, pain relief efficacy in the assessed joint must be evaluated on VAS and the patient global assessment of efficacy must be performed using a categorical scale and the time of administration of the rescue medication must be recorded.

Triamcinolone suspension for injection is provided by the study sponsor.

Name	Kenalog®
INN	Triamcinolone
Dosage form	Suspension for injection
Active substance	Triamcinolone acetonide
Excipients	Benzyl alcohol, sodium chloride, carmellose sodium, polysorbate 80, hydrochloric acid, sodium hydroxide, water for injection
Packaging	Ampoules, 40 mg/mL, 1 mL No. 5 (1 blister, 5 ampoules per blister)
Manufacturer	JSC KRKA, dd. Novo mesto, Slovenia

If an attack recurs after the use of the rescue medication, treatment is carried out in accordance with the standard practice of the hospital.

#### 9.8.3 Recording information on prior and concomitant therapy

### Prior therapy

The following information about the therapy that the patient has previously received for gout (all prior therapy for gout during the gout therapy period), as well as other prior therapy within 30 days prior to screening is recorded in the CRF:

- The names of the drugs, their doses, and the dates of use;
- The names of any investigational medicinal products used by the patient with treatment dates.

To do this, the information should be transferred from the patient's chart or case record into the CRF.

#### Concomitant therapy

Information about all concomitant therapies received by the patient from the signing of the Informed Consent Form until the completion of the study by the patient must be recorded in the source documentation and in the CRF for each patient (including information on the date of the start and end of concomitant therapy or a mark on the continuation of concomitant therapy at the last visit).

## 9.8.4 Allowed concomitant therapy

#### *Uric acid-lowering agents*

Uric acid-lowering agents are allowed provided that patients have received a stable dose of these drugs for at least 4 weeks prior to the intended date of randomization, and the dose of these drugs remains stable throughout the study.

# 9.8.5 Prohibited concomitant therapy

The following therapy is prohibited from the moment of signing the informed consent (start of screening) until the end of the study (except in cases of inefficacy of sequential therapy with the investigational product and the rescue medication):

CONFIDENTIAL P. 47 of 84

- Analgesics/NSAIDs (including selective type 2 cyclooxygenase inhibitors, analgesic antipyretics and opioids); The exception is acetylsalicylic acid at a dose of <325 mg/day, when the patient is taking it as an antiplatelet agent;
- Systemic or intra-articular corticosteroids, inhaled corticosteroids, excluding rescue medications;
- Colchicine;
- Any other biological products, excluding the investigational product;
- Any investigational medicinal product or medical device other than RPH-104;
- Herbal preparations are prohibited within 2 weeks before the first RPH-104 dose and throughout the study.
- It is prohibited to prescribe uric acid-lowering agents for the first time.

Vaccination with live vaccines is prohibited during the study participation or within 60 days after RPH-104 administration.

# 9.9 Contraception during the study

Women with child-bearing potential, as well as men who have female partners with child-bearing potential, should use highly effective methods of contraception for the entire duration of the study, and also for 60 days after the administration of RPH-104.

Highly effective methods of contraception:

- 1. Complete sexual abstinence if it is preferred by the patient and is the patient's normal lifestyle. Therefore, periodic sexual abstinence during ovulation based on symptoms, body temperature measurements, during the post-ovulation period, calendar-based methods, interrupted sexual intercourse, and combinations of these methods are not acceptable contraception methods.
- 2. Female surgical contraception: bilateral oophorectomy, tubal ligation carried out at least 6 weeks before the administration of the investigational medicinal product.
- 3. Vasectomy in men carried out at least 6 months before the administration of the investigational medicinal product, with a documented absence of sperm in ejaculate.
- 4. Use of an intrauterine contraceptive—intrauterine device (IUD): IUD made of copper or IUD with progesterone.
- 5. Double barrier method (condom and intrauterine spermicide, spermicidal cervical caps or spermicidal diaphragms).

